3.5.5.1.2 Pediatric Population

There will be no efficacy assessment in this population as enrollment in this study will be limited to pediatric subjects who were virologic failures and had emergent RAS present at FW12 in the prior treatment study.

3.5.5.2 Statistical Methods for Safety Analyses

3.5.5.2.1 Adult Population

Safety and tolerability in adult subjects will be assessed by clinical review of all relevant parameters including drug-related SAEs, ECIs, and laboratory parameters.

The number and proportion of subjects with ECIs will be tabulated. Continuous laboratory parameters will be summarized by 12-month intervals using descriptive statistics. These 12-months intervals are related to the Study Months and are determined by a set of continuous relative day ranges, calculated from study entry. Day ranges for safety evaluation are provided in [Table 8](#).

Table 8

Definition of Study Months for Safety Evaluation

Month	Relative Day Range ^a
Screening/Baseline	-91 to 30
12	-31 to 547
24	548 to 912
36	913 to 1277
48	1278 to 1642
60	≥1643

^a Day range relative to study entry, i.e. date of screening/baseline visit

Yearly changes from baseline in MELD and Child-Pugh scores will be summarized in all adult subjects using descriptive statistics. Changes in eGFR will be summarized for subjects from PN052. Descriptive statistics will be provided for the rate that subjects with CKD (PN052) require liver and/or kidney transplants.

Missing values will be handled using the Data-As-Observed approach.

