1.5.1 Adult Population

Prior to AM 03, all HCV-infected adult subjects previously treated with GZR in a prior treatment study were eligible for enrollment into PN017.

- AM 03 limited study eligibility to HCV-infected subjects who had either: 1) failed a GZR-containing therapy in a prior treatment study or 2) had CKD and received at least 1 dose of GZR in prior treatment study PN052. Starting with AM 03, the following adult subjects were discontinued from PN017 based on the new eligibility criteria: Subjects who had achieved SVR in a prior treatment study (other than PN052).
- Subjects who had failed GZR-containing therapy in a prior treatment study and received retreatment with a different HCV therapy (either prior to or during active participation in PN017).

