2.4.1.1 Adult Population

Prior to AM 03, all HCV-infected adult subjects previously treated with GZR in a Merck-sponsored clinical study (parent study) were eligible for enrollment into PN017.

Starting with AM 03, several significant changes have been made to the study design and duration:

1. New enrollment will be limited to those who failed therapy in the prior treatment study.
2. Subjects in PN017 with virologic failure at FW24 in the prior treatment study will continue for 3 years of follow-up (other than PN052 subjects) or 5 years of follow-up (PN052 subjects).
3. Subjects (other than PN052 subjects) in PN017 who entered with HCV RNA <LLoQ were discontinued after the next scheduled visit.
4. Subjects who receive a new HCV therapy regimen during PN017 will be discontinued.
5. The enrollment window is 3 months after the last visit in the prior treatment study.

There are a total of 7 study visits (11 study visits for PN052 subjects) and, as needed, a viral confirmation visit.

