2.7.2 Safety Analyses

2.7.2.1 Adult Population

The safety analyses will be based on data from all adult subjects entering the study. Long-term safety, drug-related SAEs, ECIs, any AEs related to protocol-specified procedures (blood draw), and laboratory data will be summarized for all adult subjects using descriptive statistics. Follow-up data collected after a subject started HCV treatment will be summarized separately.

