3.5.4.2 Safety Analysis Populations

3.5.4.2.1 Adult Population

All data from adult subjects who sign an informed consent/assent for this study will be included in the safety evaluation.

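### Adult ECI counts carry no time at risk although planned follow-up differs by cohort; separately, Table 8 needs a corrected Month 12 bound and a record-selection rule

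*Combined protocol and SAP*

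**What the plan says.** **ECI summary.** Section 3.5.5.2.1 states: "The number and proportion of subjects with ECIs will be tabulated". Section 2.7.2.1 lists ECIs with the other adult safety items, "and laboratory data will be summarized for all adult subjects using descriptive statistics". The population is everyone who consents (Section 3.5.4.2.1): "All data from adult subjects who sign an informed consent/assent for this study will be included in the safety evaluation".

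**Follow-up.** Section 2.4.1.1 sets different lengths from AM 03 on. Non-PN052 subjects "who entered with HCV RNA <LLoQ were discontinued after the next scheduled visit". Virologic failures continue for 3 years, or 5 years if from PN052. Also, "Subjects who receive a new HCV therapy regimen during PN017 will be discontinued"; Section 3.2.4.8.1 repeats this.

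**Partial separation.** Section 1.3 says that PN052 is assessed apart from other populations. Section 3.5.5.2.1 plans a rate of liver and kidney transplant in PN052 but gives no denominator. Section 2.7.2.1 adds: "Follow-up data collected after a subject started HCV treatment will be summarized separately".

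**Start of counting.** Footnote 3 of the adult flow chart (Section 1.7.1) limits reported ECIs to those after consent. Section 3.2.4.1 marks three pre-entry items for collection as ECIs: hepatocellular carcinoma, kidney transplant and change in eGFR. Section 3.4.3.2.1 does the same for the first two.

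**Table 8.** The windows are described as continuous from study entry. Screening/Baseline is printed as -91 to 30 and Month 12 as -31 to 547. Chemistry, hematology, coagulation and FibroTest are also drawn at Month 6 (Sections 1.7.1 and 3.3.1.1), for which Table 8 has no row.

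**The concern.** Long-term safety is adult primary objective 3, and Section 1.3.3 speaks of assessing the incidence of cardiac and neurologic events. A proportion with an event answers that only if the period of observation is known and similar across subjects. Here it varies by cohort, by HCV RNA status at entry, by date of enrolment relative to AM 03 and by retreatment. A reader who compares ECI proportions across response groups or prior studies cannot separate event frequency from time observed.

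The plan handles unequal follow-up elsewhere. Time to relapse uses Kaplan-Meier with censoring (Section 3.5.5.1.1), and Kaplan-Meier may be used for reversion to wild type (Section 3.5.5.3.1). Section 3.5 says no separate SAP will be issued, so no later plan document is due to supply a time base for ECIs.

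The Table 8 question is a separate correction. As printed, a laboratory record can belong to two windows, and a value from a subject whose last draw was at Month 6 would be reported as Month 12.

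**Working it through.** **1. Does any section supply time at risk for ECIs?**
- Section 3.5.5.2.1: number and proportion, plus a PN052 transplant rate with no stated denominator.
- Sections 2.7.2.1 and 3.5.5: data after new HCV treatment kept separate, without person-time.
- Section 3.5.5.4: disposition and baseline characteristics only.
- Section 3.5.8: summaries by prior study for relapse and resistance, with ECIs not named.

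None does, and the ECI method does not itself specify separation by follow-up cohort.

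**2. How much can follow-up alone move a proportion?** The documents give no ECI rate, number of subjects or follow-up distribution, so the rate is an assumption: constant and equal in everyone. Expected proportion = 1 - exp(-rate x T).

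| Assumed rate per 100 person-years | T = 0.5 y | T = 3 y | T = 5 y |
|---|---|---|---|
| 0.5 | 0.25% | 1.5% | 2.5% |
| 1 | 0.5% | 3.0% | 4.9% |
| 2 | 1.0% | 5.8% | 9.5% |
| 5 | 2.5% | 13.9% | 22.1% |

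Conversely, an observed 6% implies -100 x ln(0.94)/3 = 2.06 per 100 person-years over 3 years, but 1.24 over 5 years.

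**3. Is the direction known?** Suppose non-PN052 responders and failures can each leave anywhere from 0.5 to 3 years. At 1 per 100 person-years in both groups, the failure-to-responder ratio of proportions is:
- failures 3 y, responders 0.5 y: 2.96/0.50 = 5.9
- both 3 y: 1.0
- failures 0.5 y, responders 3 y: 0.50/2.96 = 0.17

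These ratios only restate the assumed follow-up times. They show that the direction is not fixed.

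**4. Precision of an incidence rate** (exact Poisson 95% limits, per 100 person-years, illustrative counts): 0 events in 100 person-years, 0 to 3.7; 5 in 500, 0.3 to 2.3; 30 in 3000, 0.7 to 1.4.

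**5. Table 8.** The upper bounds reproduce as midpoints of 365-day years, rounded down: 365 x 1.5 = 547.5 gives 547, and likewise 912, 1277 and 1642. The later lower bounds are the previous upper bound plus 1: 548, 913, 1278 and 1643. Only Month 12 breaks the pattern: 30 + 1 = 31, against -31 printed.
- Overlap as printed: 30 - (-31) + 1 = 62 days, including day 0.
- Month 12 width with 31: 547 - 31 + 1 = 517 days, against 912 - 548 + 1 = 365 for Month 24 (the same for 36 and 48).
- Month 6 visit, +/- 3 months: 182.6 +/- 91.3 = day 91.3 to 273.9, wholly inside 31 to 547. Month 12 visit: day 273.9 to 456.6.

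Correcting the bound removes the overlap but does not say which record represents Month 12. MELD and Child-Pugh have no scheduled Month 6 assessment, so their scheduled values are affected only by the overlap.

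**The case against.** The plan is not purely pooled. PN052, the longest-followed cohort, is to be assessed apart and has its own transplant rate. Five ECIs (kidney transplant, decreased eGFR, new-onset diabetes, cryoglobulinemia and post-transplantation glomerulonephritis) are confined to PN052, and data after retreatment are kept separate. No hypothesis is tested and no ECI comparison by response is planned, so harm arises only if a reader makes that comparison. Section 3.5.5.2.1 also relies on clinical review, not on the ECI table alone. The Summary of Changes shows that events between the prior study and entry were included on purpose. In Table 8, 31 is evidently the intended bound, the minus sign may be a misprint or may come from converting the PDF to text, and yearly rows were a deliberate choice.

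Most of this stands and limits the point. It does not remove it: none of these provisions supplies person-time, footnote 3 still conflicts with the pre-entry collection, and the choice among several records in a window stays open even with 31.

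A reader might infer that responders have systematically less time at risk, so that the ECI table favours or penalises them. The documents do not support that. Retreated failures also leave early, and responders enrolled well before AM 03 may have up to 3 years.

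**Conclusion.** The point holds as a gap in a descriptive safety summary. The ECI proportion is a correct count of subjects with observed events, but it is not a risk over any stated period, and the plan offers no companion measure that is. The size and direction of any distortion cannot be determined from the documents; the figures above rest on assumed constant, equal rates and assumed exit times. No test, sample size or efficacy result is affected. The change should be made because it concerns a primary objective and needs no new data.

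Two further inferences go too far: that ECIs are summarised only as one pooled figure, and that the planned proportion is invalid. The first overlooks the PN052 and post-treatment provisions, and the second confuses an incomplete summary with a wrong one.

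Table 8 is a separate correction: a 62-day overlap as printed, and a missing rule for Month 6 and other extra laboratory records.

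**What to change.** **ECIs.**
- Keep the number and proportion. Add person-years and incidence per 100 person-years with exact Poisson intervals. Count time from study entry to the first event of that type, exit or start of new HCV therapy; the last stop matches Section 2.7.2.1.
- Show this for PN052 separately and for non-PN052 subjects by HCV RNA status at entry, the TD(q) and <LLoQ strata already in Section 3.5.5.4.
- State that a single rate assumes a roughly constant hazard. Where numbers allow, add cumulative incidence at fixed times.
- Use PN052 subjects as the denominator for PN052-only ECIs. Restrict graft rejection and post-transplantation glomerulonephritis to transplanted subjects (from PN052 for the latter).
- Reconcile footnote 3 with Sections 3.2.4.1 and 3.4.3.2.1. List pre-entry events apart, and exclude a subject with a pre-entry event of a given type from the risk set for that type's first-event rate.

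**Table 8.**
- Correct the Month 12 lower bound, apparently 31.
- Then either add a Month 6 row (day 31 to 274, with Month 12 as 275 to 547), or keep yearly rows and use for Month 12 the record nearest day 365 among days 275 to 547. Day 274 lies at the edge of both visit windows, so the cut is a convention.
- State one record-selection rule for all windows, including early-discontinuation draws.

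**Cost.** SAP wording and a few tables from data already collected. The safety output becomes slightly longer, and intervals will be wide in small groups.

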1.3 SUMMARY OF RATIONALE

The HCV clinical development program has evaluated GZR in combination with pegylated-interferon, ribavirin, and other direct-acting antiviral (DAA) therapies, including elbasvir (EBR), ruzasvir (RZR), and uprifosbuvir (UPR) as various investigational HCV treatment regimens. Refer to the respective Investigator Brochures (IBs) for background information and study results for the various GZR-containing regimens.

Across the program, over 4,500 HCV-infected subjects will have received at least 1 dose of GZR in more than 20 Phase 2 and Phase 3 Merck-sponsored clinical studies (hereafter referred to as prior treatment study). The totality of Phase 2 and Phase 3 data was used to identify a highly effective combination of DAAs for the treatment of chronic HCV. During the course of development, different regimens, treatment durations, and genotypes (GTs) were assessed. Ultimately, these data were used to support the approval of the combination regimen EBR/GZR for 12 to 16 weeks in GT1 and GT4.

This study (Protocol 017; PN017) will assess: 1) durability of virologic response, 2) monitor persistence of virologic resistance, and 3) safety, including progression of liver disease, and for subjects with chronic kidney disease (CKD) from PN052, progression of kidney disease.

Enrollment in PN017 includes an adult population (aged ≥ 18 years) and a pediatric population (aged 3 to < 18 years), based on subject age at the time of screening in the prior treatment study. While many studies are grouped together for objectives and analyses, two studies (PN052 and PN079) enrolled special populations that will be assessed apart from other populations. Subjects from PN052 all have advanced CKD (Stages 4 or 5); these subjects are followed for 5 years to understand the natural history of CKD and liver disease progression following HCV therapy. Subjects from PN079 are pediatric subjects who will be followed only if the subject experiences virologic failure with 1 or more treatment emergent RASs.

A list of abbreviations used within this protocol is in Appendix 6.3.

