¹ Visits should be scheduled as close to the indicated study period as possible. Visit windows are +/- 3 months. All visits should be recorded on the actual date that they occur and any missed or late visits must be documented accordingly. ² Participation in FBR is voluntary and is not required in order to participate in the study. ³ Protocol specified ECIs, AEs related to protocol-specified procedures (blood draw), and drug related new Serious Adverse Events, which occur following enrollment in the present study (after Informed Consent Form is signed) will be reported. ⁴ If a subject is directly entered into this long-term follow-up protocol on the same day as the last study day of the prior treatment study, since these visits have different laboratory requirements, the lab kit for each of the two visits must be used. Samples are collected for each study separately at the same visit. (See section 3.2.4.1) ⁵ Subjects who achieved SVR in previous study and who are tested in this study and found to have HCV RNA \geq 1000 IU/mL, will have their Viral Resistance sample tested. ⁶ HCV sequence analysis will be performed, as appropriate, and will depend on the HCV-RNA level results. ⁷ Informed consent for future biomedical research samples must be obtained before the DNA and plasma samples are collected. ⁸ The screening visit should occur within 3 months of the last visit of the previous protocol. ⁹ Subjects who had HCV RNA < LLoQ at the end of follow-up in the original treatment protocol and who are tested and have HCV-RNA \geq LLoQ during this study will have their HCV Genotype obtained. If a subject has HCV RNA \geq LLoQ at Visit 1, an HCV Genotype must be performed at that visit. ¹⁰ If the unscheduled visit is being performed for follow-up of an AE/SAE (as defined in this protocol), a directed physical exam and safety labs should also be performed at this visit. ¹¹ For subjects in the 3 year follow-up who discontinue early, a Visit 7 (Month 36) Visit should be completed as the early discontinuation visit. For subjects in the 5 year follow-up (eg. PN052) who discontinue early, a Visit 11 (Month 60) visit should be completed as the early discontinuation visit. ¹² Refer to Section 3.2.4.1 for required medical history. ¹³ Visits 8, 9, 10, and 11 will only be performed if subjects were in PN052 as their parent study.												

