3.2.4.8.1 Discontinuation/Withdrawal Criteria

With the exception of subjects previously enrolled in PN052, if a subject is discontinued early from the study the subject should complete their last visit as Visit 7 (Month 36). If a subject from PN052 is discontinued early from the study, the subject should complete their last visit as Visit 11 (Month 60).

A subject will be discontinued from the study for any of the following reasons:

- The Investigator feels that it is in the best interest of the subject to discontinue.
- Request of the subject/subject's legally acceptable representative (subject/subject's legally acceptable representative has the right to discontinue from the study at any time for any reason).
- Following AM 03 all subjects (except PN052) who entered PN017 with HCV RNA TND or TD(u) were discontinued. For these subjects, participation was discontinued at the next scheduled visit for each subject.
- Following AM 03, all subjects who initiated HCV treatment after enrollment in PN017 were discontinued.

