3.3 DURABILITY, VIRAL RESISTANCE, AND SAFETY MEASUREMENTS

3.3.1 Clinical and Laboratory Measurements for Durability, Viral Resistance, and Safety

3.3.1.1 Adult Population

The primary measurement for durability of response in this study is repeat HCV RNA measurements at all study visits. Resistance will be assayed by sequence analysis, and safety will be assessed by directed physical exam, standard laboratory safety tests, and collection of ECIs, any AEs related to protocol-specified procedures (blood draw), and drug related SAE's at each visit as specified in the study flow chart in Section 1.7.1.

Clinical Evaluations

- Directed Physical Examination: Yearly as described in the flow chart.
 - The examination must be performed by the Principal Investigator or Sub-Investigator (physician, physician assistant or nurse practitioner) listed on FDA Form 1572 or *equivalent document*.
- Collection of therapies used for the treatment of HCV: All visits.

NOTE: Following AM 03, all subjects who initiated HCV treatment after enrollment in PN017 were discontinued.

- Childs-Pugh Score: Computed from safety laboratory data and clinical assessment obtained at baseline and every year for adult subjects
 - <http://www.mdcalc.com/child-pugh-score-for-cirrhosis-mortality/>
- Blood pressure and heart rate
- Weight and height

- Review procedure related AEs, ECIs, and drug-related SAEs

Unscheduled Visits:

- Unscheduled visits may be performed at any time at the discretion of the Investigator.

Laboratory Safety Evaluations

The following will be collected (as defined in Section 2.6.1):

- Chemistry (Abbreviated Non-fasting), hematology, and coagulation panel-collected yearly, with an additional collection at 6 months;
- MELD score (with and without dialysis): Computed from safety laboratory data obtained at baseline, and every year for all adult subjects (at the time of entry in the prior treatment study).
- Fibrosure® (Fibrotest®) - collected at 6 months post study entry and then yearly beginning at 12 months in all adult subjects (at the time of entry in the prior treatment study); and
- eGFR (collected yearly in PN052 subjects only).

HCV Evaluations

- HCV RNA quantitation - collected at all visits;

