3.5.8 Subgroup Analyses and Effects of Baseline Factors

The time to viral relapse in adult subjects will be summarized for categories of classification variables, shown to be associated with response such as genotype. Time to viral relapse and antiviral resistance will be summarized based upon the prior treatment study in which GZR was administered.

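### Adult safety summaries over time are not split by prior study, although the later rows are essentially PN052 only and Section 1.3 says PN052 is assessed apart

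*Combined protocol and SAP*

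**What the plan says.** Section 3.5.5.2.1 contains two statements about adult time courses. For laboratory data: "Continuous laboratory parameters will be summarized by 12-month intervals using descriptive statistics". For liver scores: "Yearly changes from baseline in MELD and Child-Pugh scores will be summarized in all adult subjects". Table 8 in the same section defines yearly windows from baseline to Month 60, and missing values are left as observed. The only safety outputs given for PN052 alone are eGFR change and the rate of liver or kidney transplant. Section 3.5 states that no separate SAP will be issued, so this text governs.

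Other sections bear on who contributes to each row:

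- Section 1.3: "two studies (PN052 and PN079) enrolled special populations that will be assessed apart from other populations". It also states that every PN052 subject has CKD stage 4 or 5.
- Section 1.7.1, footnote 13: "Visits 8, 9, 10, and 11 will only be performed if subjects were in PN052 as their parent study". The blood-volume table in Section 6.2.1 agrees for Months 42 to 60.
- Section 3.2.4.8.1: "Following AM 03 all subjects (except PN052) who entered PN017 with HCV RNA TND or TD(u) were discontinued". There and in Section 2.4.1.1, the exit is placed at each subject's next scheduled visit.
- Section 3.2.4.6: after Amendment 03, PN059 subjects no longer need follow-up past Year 3. This implies that such follow-up was once planned.
- Section 3.5.8: "Time to viral relapse and antiviral resistance will be summarized based upon the prior treatment study in which GZR was administered". Safety, laboratory and liver-score outputs are not listed there.

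**The concern.** The yearly rows are meant to be read in sequence, but they do not describe the same people. Up to Month 36 they mix PN052 with everyone else. From Month 48 they are essentially PN052. In between, Amendment 03 removed the non-PN052 subjects who had entered below LLoQ, so the mix also moves earlier.

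Observed-data summaries do nothing to correct for this. For a parameter tied to kidney function, such as creatinine or urea nitrogen (both in the panel in Section 2.6.1), a pooled level would step at Month 48 because the patients differ, and the step would look like deterioration.

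Long-term safety is the third primary objective for adults, and liver function by MELD or Child-Pugh is the first exploratory one. Without a split, a reader of the tables cannot separate CKD from non-CKD subjects, or, outside PN052, those who entered below LLoQ from those who entered with quantifiable virus.

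**Working it through.** The documents give no sample size, no PN052 share and no count of Amendment 03 exits (Section 3.5.7 leaves the sample size open). There is therefore no plan figure for the size of this effect to reproduce. The windows can be checked exactly; the rest is mixture arithmetic under stated assumptions.

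**1. Can a three-year subject fall in the Month 48 row?** With a month of 365.25/12 = 30.4375 days, the midpoints between yearly visits are:

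- 18 × 30.4375 = 547.9
- 30 × 30.4375 = 913.1
- 42 × 30.4375 = 1278.4
- 54 × 30.4375 = 1643.6

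These reproduce the Table 8 boundaries 547/548, 912/913, 1277/1278 and 1642/1643. A Month 36 visit at the late edge of the ±3-month window falls at 39 × 30.4375 = day 1187.1, before day 1278. In-window visits of three-year subjects therefore never reach the Month 48 row. The exceptions are out-of-window or unscheduled visits and any PN059 data collected past Year 3 before Amendment 03.

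**2. PN052 share by row.** Let p be the PN052 share at entry, q the non-PN052 failures, s = 1 − p − q the non-PN052 SVR subjects, and r the fraction of the SVR group still present. The PN052 share is p / (p + q + s·r). Assumed, not in the documents: p = 5% to 20%, q = 5% to 15%, and r = 0.9–1.0, 0.5–0.8 and 0.2–0.5 at Months 12, 24 and 36.

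| Row | PN052 share |
|---|---|
| Baseline | 5–20% |
| Month 12 | 5–22% |
| Month 24 | 6–32% |
| Month 36 | 8–50% |
| Months 48, 60 | 100% (ignoring the exceptions above) |

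The Month 36 extremes are 0.05 / (0.05 + 0.15 + 0.80 × 0.5) = 0.083 and 0.20 / (0.20 + 0.05 + 0.75 × 0.2) = 0.50.

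**3. Laboratory parameter summarised as a level.** Suppose PN052 differs from the others by D units (of either sign) and nobody changes. The pooled mean minus the non-PN052 mean equals share × D. That is 0.05–0.20 D at baseline, 0.08–0.50 D at Month 36 and 1.00 D at Month 48. The whole movement comes from who is present.

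**4. MELD and Child-Pugh, summarised as change from baseline.** If nobody changes, each subject contributes 0 and the pooled mean change is 0 in every row, whoever remains. A distortion needs unequal rates. Assume a rise of 0.5 points per year in PN052 and 0 elsewhere:

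- Month 36, pooled: 0.5 × 3 × share = 1.5 × 0.083 = 0.125, up to 1.5 × 0.50 = 0.75.
- Month 48, pooled: 0.5 × 4 × 1.00 = 2.0.
- Apparent step over that year: 2.0 − 0.75 = 1.25, up to 2.0 − 0.125 = 1.875.
- Step within PN052: 2.0 − 1.5 = 0.5.

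Unequal rates are plausible. Section 3.3.1.1 specifies "MELD score (with and without dialysis): Computed from safety laboratory data obtained at baseline", so dialysis status enters the score, and PN052 is the cohort in which dialysis and kidney progression are tracked.

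**The case against.** The best defence has five parts.

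**Change scores resist turnover.** A reader might infer that the MELD and Child-Pugh trends simply show who remains. The documents do not support that: both are specified as changes from baseline, and step 4 of the working gives zero when nobody changes. This part of the defence stands in full.

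**Pooling is not certain.** Section 1.3 promises that PN052 is assessed apart, and the reference to all adults in Section 3.5.5.2.1 may only say who is scored, in contrast to eGFR, which is for PN052. That reading is possible, but the operative text does not carry the promise through, and Section 3.5.8 omits safety from the summaries by prior study. Data after new HCV treatment are summarised separately (Sections 2.7.2.1 and 3.5.5), but that split is a different one. Nor does the plan say outright that laboratory data are tabulated as levels; it says descriptive statistics. Since the next paragraph specifies change from baseline for the scores and this one does not, levels are the natural reading.

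**The earlier shift is unknown.** A reader might also infer that PN052 dominates the rows soon after Amendment 03. That would require every non-PN052 SVR subject to have gone. Exits came at each subject's next visit, hence at differing study months, and some may already have completed Year 3. The documents do not settle the mix at Months 24 and 36.

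**Some of the material is already planned.** MELD is already scored with and without dialysis, and bilirubin, INR and albumin are already in the yearly panel. Formally restricting Months 48 and 60 to PN052 would change almost nothing, since the design already does so.

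**Nothing is tested.** Section 3.5.5 rules out hypothesis tests, so no error rate is affected. This is correct; what suffers is interpretation.

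**Conclusion.** The point holds in a limited form. Sections 1.3 and 3.5.5.2.1 are not reconciled: the promise to assess PN052 apart reaches the adult safety analysis only for eGFR and transplants.

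For laboratory parameters summarised as levels, the move to essentially PN052-only rows at Month 48 can produce a trend with no individual change. Under an assumed PN052 share of 5–20% at entry, 80–95% of the PN052-versus-other difference D would appear between baseline and Month 48 (1.00 D less 0.20 D or 0.05 D). D itself is not in the documents.

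For MELD and Child-Pugh the weakness is conditional: the pooled yearly trend misleads only if PN052 and the other subjects change at different rates. The 1.25 to 1.875 step shows what one assumed pair of rates would do and is not a prediction.

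The change is worth making before tables are produced, because a primary safety objective is read from them and the remedy needs no new data.

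**What to change.** In Section 3.5.5.2.1, bring the text into line with Section 1.3:

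- Present laboratory, MELD and Child-Pugh summaries separately for PN052 and non-PN052 subjects. Split the non-PN052 group by HCV RNA status at entry, a split that Section 3.5.5.4 already uses for the baseline tables.
- At each visit show n and the baseline mean of the subjects contributing to that row.
- State whether laboratory parameters are tabulated as levels, as changes from baseline, or both.
- End any pooled adult summary at Month 36 and label the Month 48 and Month 60 rows as PN052. State how late visits and any PN059 data from before Amendment 03 are handled.

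The cost is a few sentences of SAP text and a few more table columns, all from data already collected. The drawback is smaller cells, perhaps thin ones for non-PN052 subjects who entered with quantifiable virus.
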